Our overriding hypothesis is that radiation interacts, enhances, and potentially accelerates the individual patient's genetic predisposition to develop breast cancer, but does not fundamentally alter the molecular phenotype. To test this hypothesis, we plan to obtain the 54 (or more if available) formalin-fixed, paraffin-embedded tissue samples of the secondary breast cancer cases from the CCSS bio-repository from women who received thoracic radiation. We plan to subject these samples to RNA extraction, using established protocols that yield expression profiles that are highly concordant with frozen tissue.¹²⁻¹³ This mRNA will then be assayed for quality and quantity and amplified accordingly.¹⁴ The resultant cDNA will then be hybridized, at our core facility, using the Affymetrix U133A gene chip. Using the GeneSpring software platform, gene expression data will then be analyzed using supervised methods (which will query the expression levels of specific, hallmark genes that define the molecular subtypes of breast cancer) as well as unsupervised methods (within the set of 54 cases as well as in conjunction with 1,619 general population cases) to determine the prevalence of known, and potentially novel, molecular subclasses of these secondary tumors. Once the subclass designation is established for the 54 secondary breast cancers, the patient demographics and overall survival time after diagnoses will be compared to their spontaneous/general population

counterparts. Generating this working data will enable us to answer the following clinically important questions, which represent our specific aims:

- Specific Aim 1: What is the prevalence/distribution of Luminal A, Luminal B, Basal, Her2-enriched and breast-like breast cancer subtypes among those women who received thoracic radiation during childhood for their pediatric malignancy versus that observed in the general population of spontaneous breast cancers? Consistent with our overriding hypothesis is that the prevalence of these molecular subtypes will approximate that observed in the general, spontaneous breast cancer population. Therefore, assuming radiation induced breast cancers are representative of the general population, approximately 50% will be Luminal A, 20% will be Luminal B, 20% will be Basal, and 10% will be Her 2+.

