The first layer of analysis will consist of determining the distribution of the molecular subtypes of the secondary breast cancers. The RNA will be isolated from the study samples and in a manner similar to the clustering analysis of the control population, the gene expression status of the 249 genes that define the molecular subclasses will be performed in an unsupervised manner on the 54 study and 1,619 control cases together. To account for batch-effect and paraffin extraction, log-transformation and normalization using the RMA method will be performed, again using GeneSpring software, with all cases included. Genes will undergo an independent QA process (to determine if there is signal susceptibility to the formalin fixation and parafinization process) and will be excluded from the final clustering analysis. The placement of the study cases within the cluster groups, as defined predominantly by the control population, will determine the subclass assignment. A chi-square test will be used to compare the distribution of molecular subtypes between the primary and secondary breast cancers.

The raw data from the .cel files of the study population will also be compared. This will be especially important in the event of the formation of a separate clustering group by the radiation-induced cases and a novel subtype is identified. From this analysis, the genes that define this new subclass will be identified and reported. This approach will also allow the identification of gene expression, unique to previously radiated breast tissue, which spans across all subtypes.

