The CCSS database represents the only chance in which the issue of the breast cancer molecular subclass prevalence, in the setting of previous thoracic radiation, could possibly be addressed. If any single institution attempts to do this, there would not be enough cases to draw a statically significant conclusion. Fortunately, there are 54 cases within the CCSS database, and this is sufficient to determine if the 5 molecular subtypes are evenly distributed, or predominately composed of 1 or 2 subtypes. In the most diffuse scenario, if there are at least 10 samples per subtype (5), there will be a >80% power to detect a 2-fold difference between any of the two groups using Chi-squared analysis. A coefficient of variation of 50% and alpha = 0.005 (.05/10, to adjust for 10 comparisons between 5 groups) will be used for the calculations. Since we expect there to be 50% with the Luminal A subtype designation, there will be even greater power to make this conclusion statistically valid. It should be iterated, though, that regardless of statistical power, this is a retrospective study and the large number of subjects from the CCSS provide the only means for attempting to answer this scientific question.

Figures:

Hierarchical clustering of 115 tumour tissues and seven non-malignant tissues using the "intrinsic" gene-set. (A) A scaled-down representation of the entire cluster of 540 genes and 122 tissue samples based on similarities in gene expression. (B) Experimental dendrogram showing the clustering of the tumours into five subgroups. Branches corresponding to tumours with low correlation to any subtype are shown in grey. (C) Gene cluster showing the *ERBB2* oncogene and other co-expressed genes. (D) Gene cluster associated with luminal subtype B. (E) Gene cluster associated with the basal subtype. (F) A gene cluster relevant for the normal breast-like group. (G) Cluster of genes including the oestrogen receptor (*ESRI*) highly expressed in luminal subtype A tumours. Scale bar represents fold-change for any given gene relative to the median level of expression across all samples. PNAS, July 8, 2003, vol. 100, no. 14, 8418–8423. Copyright (2003) National Academy of Sciences, USA.

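### The 54 cases are justified by evenness within the cases and by subtype-against-subtype comparisons, so the stated power is not that of the planned comparison with the 1,619 controls

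*Protocol*

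**What the plan says.** Specific Aim 1 asks for the subtype distribution in irradiated women against that in the general population. Its hypothesis is that the prevalence of the "molecular subtypes will approximate that observed in the general, spontaneous breast cancer population". It gives the expected figures if that holds: "approximately 50% will be Luminal A, 20% will be Luminal B, 20% will be Basal, and 10% will be Her 2" positive. The primary endpoint, under Outcome of interest, is likewise a comparison with spontaneous cancers.

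The first-layer paragraph of Statistical and Analytic Plans clusters the genes "on the 54 study and 1,619 control cases together" and names one test: "A chi-square test will be used to compare the distribution of molecular subtypes between the primary and secondary breast cancers". It states no alpha for that test.

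The last paragraph of the same section justifies the sample of 54 with the claim that "this is sufficient to determine if the 5 molecular subtypes are evenly distributed, or predominately composed of 1 or 2 subtypes". It then takes at least 10 samples in each of five subtypes and says "there will be a >80% power to detect a 2-fold difference between any of the two groups using Chi-squared analysis". The inputs are a coefficient of variation of 50% and alpha 0.005, which is 0.05 divided by ten pairwise comparisons of five groups. It adds that an expected 50% Luminal A makes the power greater still.

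**The concern.** The adequacy claim answers a question that Aim 1 does not ask. Whether the subtypes are even within the cases can be judged without any control, whereas Aim 1 cannot. The protocol's own no-effect mix is already dominated by one or two subtypes. That pattern therefore fits the overriding hypothesis, and it equally fits the listed alternative that radiation induces one particular subtype.

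The power figure has the same gap: neither the 1,619 controls nor the 50/20/20/10 reference is among its inputs. This matters because the hypothesis is one of similarity. A non-significant chi-square will be tempting to read as confirmation, and a general statement of more than 80% power for 2-fold differences encourages that reading.

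**Working it through.** **Inputs from the protocol.** 54 cases; 1,619 controls; no-effect shares 50/20/20/10 (Aim 1); 10 per subtype, 2-fold difference, coefficient of variation 50%, alpha 0.005 (last paragraph of Statistical and Analytic Plans).

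**Assumptions.** Two-sided tests. Alpha 0.05 for the primary chi-square, with 0.005 also shown. The four stated shares sum to 100%, so the fifth (breast-like) subtype has no stated share; 0–15% is tried, with the other shares scaled down.

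**1. The plan's own figure.** Five subtypes give 10 pairs, and 0.05/10 = 0.005 is right. The power depends on how the statement is read.

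- *Proportions, 10 v 10.* Power = Φ{[|p₂−p₁| − z√(2p̄(1−p̄)/n)] / √([p₁(1−p₁)+p₂(1−p₂)]/n)}, with z = 2.807 and n = 10.
  - 20% v 40%: (0.200 − 2.807×0.2049)/0.200 = −1.88, giving 3%.
  - 40% v 80%: 14%.
  - 50% v 100%, the most favourable case: 39%.
- *Counts of 10 v 20.* (20−10)²/30 = 3.33 on 1 df, giving 16%.
- *Two means, constant SD equal to half the lower mean.* Standardised difference 1/0.5 = 2. Then 2×√(10/2) − 2.807 = 1.67, giving 95% by z, or 88% by t.
- *Two means, SD proportional to each mean.* 39% (t) to 51% (z).

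So more than 80% is not reached by the chi-squared analysis the sentence names. Among these readings it is reached only as a comparison of two means with constant SD.

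The premise of 10 per subtype also conflicts with the expected mix. Her2 at 10% gives 54×0.10 = 5.4 expected cases, and the chance of 10 or more is about 4%.

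**2. Evenness when radiation changes nothing.** Goodness-of-fit against equal shares, noncentrality 54×Σ(p−1/k)²/(1/k).

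- Four classes: (0.0625+0.0025+0.0025+0.0225)/0.25 = 0.36; 54×0.36 = 19.4 on 3 df.
- Five classes, fifth empty: (0.09+0+0+0.01+0.04)/0.20 = 0.70; 54×0.70 = 37.8 on 4 df.

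Simulated rejection of evenness:

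| Mix | alpha 0.05 | alpha 0.005 |
|---|---|---|
| Four classes | 96% | 83% |
| Five, breast-like 0% | about 100% | about 100% |
| Five, breast-like 5% | 99.6% | 96% |
| Five, breast-like 10% | 97% | 86% |
| Five, breast-like 15% | 92% | 74% |

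In samples from 50/20/20/10 the two largest subtypes together exceed half of the cases practically always. Now exchange the Luminal A and Basal shares (20/20/50/10), a drastic change. The evenness calculation is identical (97% asymptotically), while the 54 v 1,619 test would detect the change with 99.9% power.

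**3. The planned test, 54 v 1,619.** Noncentrality is [54×1,619/1,673]×Σ(p₁−p₀)²/p̄ = 52.26×Σ(p₁−p₀)²/p̄, where p̄ is the pooled share. Example, Basal doubled with the other shares scaled pro rata (37.5/15/40/7.5): Σ = 0.244, noncentrality 12.8 on 3 df, 86% asymptotically and 81% simulated. The table gives simulated power at alpha 0.05 with four classes and perfect classification; null rejection was about 5%.

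| Shift in the cases | Power |
|---|---|
| Luminal A 50 to 25% | 91% |
| Basal or Luminal B 20 to 40% | 81% |
| Luminal A 50 to 70% | 65% |
| Her2 10 to 20% | about 48% |
| Basal 20 to 30% | 29% |
| Basal 20 to 10% | 28% |
| Her2 10 to 5% | 9–10% |

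**4. How firm is the 81%?** For Basal doubled:

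- fifth subtype at 5% or 10%: 74% or 71%
- 45 or 40 evaluable samples (assumed): 74% or 69%
- 10% uniform misclassification (assumed): 69%
- alpha 0.005: 57%

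**The case against.** The strongest reply is that the evenness sentence is a rationale and not a decision rule. That stands. A reader might infer that the study would declare a radiation effect whenever one or two subtypes predominate. The protocol does not support this: inference on Aim 1 rests on the case-control chi-square, which holds its error rate at about 5%, and about 50% Luminal A is explicitly the result expected if the hypothesis is right.

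Second, comparisons between subtypes within the cases do have a place. Aim 2 relates subtype to survival and other factors with t-tests, log-rank tests and Cox models, and a coefficient of variation with 10 per group suits a comparison of means. This also stands in part. It could explain where the figure came from, although the ten pairwise tests are not listed there, and it does not make the figure the power for Aim 1.

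Third, the sample is every available case, and the protocol says the question is worth attempting regardless of power. That explains why the number is 54. It does not make the sufficiency claim correct.

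Two further readings go too far. One is that the sample is inadequate throughout: large shifts in common subtypes have reasonable power. The other is that a doubling of Basal or Luminal B is simply detectable: the 81% needs four classes, all 54 samples evaluable, no misclassification and alpha 0.05, whereas the plan counts five subtypes and uses paraffin-embedded tissue.

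**Conclusion.** The point holds as a mismatch between the sample-size justification and the primary analysis. Under the protocol's own no-effect mix, evenness is rejected in about 92–100% of samples at 0.05, or 74–100% at 0.005, for a breast-like share of 0–15%. It therefore cannot tell an effect of radiation from none. The stated power belongs to other groups and another alpha, and the chi-squared method it names does not yield it.

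For the planned test, only large shifts in the common subtypes reach roughly 70–90% power. A 2-fold change in Her2 in either direction, or a halving of Basal, would be missed more often than found. These figures treat 50/20/20/10 as the control mix. The protocol gives it only as approximate, and the observed control composition is in Figure 2, which is not shown in the text available here. They also depend on which subtypes lose share. The planned test, the endpoint and the sample are not themselves invalidated.

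**What to change.** In the last paragraph of Statistical and Analytic Plans, delete the evenness-or-predominance sentence and the ten-comparison power figure as the justification for Aim 1. If the pairwise figure was meant for Aim 2, move it there with the test it belongs to.

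In their place, give the power of the planned chi-square for 54 cases against 1,619 controls. The null should be the observed control distribution in Figure 2 and the alpha should be stated. Cover a range of shifts, fifth-subtype shares and numbers of evaluable samples. State three things:

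- Only large shifts in the common subtypes reach roughly 70–90% power.
- 2-fold changes in Her2 and a halving of Basal would usually be missed.
- A non-significant chi-square does not establish that the distributions are the same.

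The cost is some rewording and a short simulation. The stated power becomes less favourable; no extra samples are needed.

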 - e. Primary and secondary breast cancer with any hormone status, including ER+, PR+/-, Her2neu-; ER+,PR+/-, Her2neu +; ER-,PR-, Her2neu-; ER-/PR-, Her2neu +

Exclusion criteria

- 1. Previously published research using gene expression data sets for primary breast cancers previously treated with chemotherapy, hormone therapy, or radiation prior to analysis will not be used for the control population
- 2. Previously published research using gene expression data from cell lines and animal studies will not be used for the control population
- 3. Non-epithelial breast malignancies, including lymphoma or sarcoma of the breast and melanoma and non-melanomatous skin cancers
- 4. In situ carcinomas of the breast

Materials/Data needed from the CCSS

- 1. Adequate secondary breast cancer tissue, from the study patients, to yield sufficient, amplifiable mRNA for eventual hybridization with the Affymetrix U133A Gene Chip.
 - a. N=54 (or more if possible)
 - b. At least five 10-micron scrolls (or equivalent quantity) of tumor tissue, verified by corresponding H&E slide, for each sample
- 2. Clinical data on study patients:
 - a. Age at childhood cancer diagnosis
 - b. Childhood primary tumor diagnosis
 - c. Childhood radiotherapy details (including total body irradiation and pelvic radiotherapy)
 - i. Dose and fractionation to irradiated site

- ii. Radiation dose to the chest
- iii. Age at start of radiation
- d. Age at breast cancer diagnosis
- e. Menopausal status at breast cancer diagnosis
- f. Age at death or last follow-up with current vital status for survival calculations
- g. Use of chemotherapy for treatment of the primary cancer

Statistical and Analytic Plans:

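### The protocol's only power figure assumes at least 10 cases in each of five subtypes, which 54 cases deliver at most 2.7% of the time and which its own expected distribution does not produce

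*Protocol*

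**What the plan says.** The power paragraph of Statistical and Analytic Plans opens by declaring the number adequate: "Fortunately, there are 54 cases within the CCSS database, and this is sufficient to determine if the 5 molecular subtypes are evenly distributed". The support is one calculation, introduced by "In the most diffuse scenario, if there are at least 10 samples per subtype (5". It claims more than 80% power for a two-fold difference between any two groups by chi-squared test, with a coefficient of variation of 50% and alpha 0.005 for ten pairwise comparisons. It adds that power will be greater still because half the cases are expected to be Luminal A.

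Specific Aim 1 expects 50% Luminal A, 20% Luminal B, 20% Basal and 10% Her2. These sum to 100% over four subtypes.

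The number 54 appears in two roles:

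- **Samples to be obtained.** The methods text under the specific aims says "we plan to obtain the 54 (or more if available) formalin-fixed, paraffin-embedded tissue samples", followed by "This mRNA will then be assayed for quality and quantity and amplified accordingly". Item 1 of Materials/Data needed from the CCSS asks for "N=54 (or more if possible" under the heading requirement "Adequate secondary breast cancer tissue, from the study patients, to yield sufficient, amplifiable mRNA".
- **Cases analysed.** Statistical and Analytic Plans clusters the "54 study and 1,619 control cases together", and the power paragraph uses the same number.

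No failure rate or evaluable number is given.

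**The concern.** Five groups of at least 10 need 50 usable cases, so 54 leaves room for only four cases of unevenness. Equal true shares do not give equal observed counts, so a diffuse distribution does not by itself deliver 10 per subtype. The protocol's own expectation is also far from diffuse. If the condition almost never holds, the one numerical statement behind the sufficiency claim describes a study that will not be run.

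The figure is also attached to the wrong comparison. It concerns pairs of subtypes within the cases, whereas the stated primary comparison is a chi-square of the subtype distribution between cases and controls. A reader who wants to know what the primary analysis can detect finds no figure for it.

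**Working it through.** **Inputs from the protocol.** 54 cases; 1,619 controls; five subtypes; at least 10 in each; alpha 0.05/10; expected shares 50/20/20/10%.

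**1. The plan's own figures.** The number of pairs is 5 × 4/2 = 10, and 0.05/10 = 0.005, as stated. The power above 80% has no unique reproduction, because a coefficient of variation is not an input to a chi-squared test. Two-sided, with 10 per group:

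- Means 1 and 2, common SD 0.5: 1/(0.5 × √(2/10)) = 4.47; 4.47 − 2.81 = 1.66; power 95% (normal), or 88% with a t test.
- CV of 50% in each group: 51% (normal) or 39% (t).
- Log scale: 68% (normal) or 55% (t).
- Chi-squared test of two proportions, 10 v 10: from 1% (10% v 20%) to 39% (50% v 100%).

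So the claim can be met under one reading, given 10 per group. The rest of the check concerns that condition.

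**2. Probability of the condition with equal shares.** P = Σ 54!/(x₁!…x₅!) × 0.2⁵⁴ over all counts of at least 10 that sum to 54. These are the ways to place the four cases above 50:

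| Extras over the five cells | Arrangements | Total probability |
|---|---|---|
| 4,0,0,0,0 | 5 | 0.0014 |
| 3,1,0,0,0 | 20 | 0.0070 |
| 2,2,0,0,0 | 10 | 0.0038 |
| 2,1,1,0,0 | 30 | 0.0124 |
| 1,1,1,1,0 | 5 | 0.0023 |

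The sum, before rounding, is 0.0268, or 2.7% (simulation: 2.69%). The median size of the smallest subtype is 7. Equal shares maximise this probability, so 2.7% is an upper bound for 54 cases.

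| Analysed | 49 | 50 | 51 | 52 | 53 | 54 | 55 | 60 | 80 | 90 |
|---|---|---|---|---|---|---|---|---|---|---|
| P(all five ≥ 10) | 0 | 0.05% | 0.25% | 0.70% | 1.5% | 2.7% | 4.4% | 19% | 86% | 96% |

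**3. Under the protocol's expected distribution.** 54 × (0.5, 0.2, 0.2, 0.1) = 27, 10.8, 10.8 and 5.4. The fifth subtype has no share, so the five-group condition has probability zero. Even all four subtypes reaching 10 has probability 0.8%.

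For the claim of greater power, the equivalent equal group size for a pair is 2ab/(a + b):

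- 27 v 10.8: 15.4
- 10.8 v 10.8: 10.8
- 27 v 5.4: 9.0
- 10.8 v 5.4: 7.2

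The three pairs with Her2 fall below 10 and the four pairs with the fifth subtype are empty. Seven of the ten planned comparisons are therefore worse placed than the premise, not better.

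**4. Loss before analysis.** The protocol gives no rate, so these are assumptions. P(at least 50 of 54 usable) is 87% at 5% loss, 36% at 10%, 8% at 15% and 1% at 20%.

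**5. The primary case-versus-control chi-square.** Simulated on four subtypes, controls at 50/20/20/10%, alpha 0.05. The alternatives are illustrative and not the protocol's. In the first three rows the other subtypes shrink or grow in proportion.

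| Alternative among cases | n = 54 | n = 49 | n = 43 |
|---|---|---|---|
| Basal 20% to 40% | 81% | 77% | 72% |
| Luminal A 50% to 30% | 72% | 68% | 62% |
| Her2 10% to 25% | 77% | 74% | 69% |
| Basal 20% to 40%, all taken from Luminal A | 88% | 85% | 80% |

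**The case against.** **The premise is conditional.** The sentence says if, and 54/5 = 10.8 is the expected count under an even spread. Quoting power at expected group sizes is common, and a split of 9/11/11/11/12 fails the threshold with almost no change in power. This stands in part: missing the threshold does not by itself collapse power, and 2.7% should not be read as a measure of lost power. It does not rescue the paragraph, which uses the condition to call 54 sufficient and then claims more power under an uneven split that breaks it.

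**Greater power may refer to something else.** The sentence about Luminal A could mean power to show that the subtypes are not evenly distributed, which a 50% share would indeed help. That is not the calculation given, which is for ten pairwise comparisons at alpha 0.005.

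**Loss of cases is not shown.** A reader might infer that the primary test will run on fewer than 54 cases. The protocol does not support that as fact. It asks for 54 or more, and the request can be read as 54 already adequate samples, since it requires tissue "to yield sufficient, amplifiable mRNA for eventual hybridization with the Affymetrix U133A Gene Chip". It does not say whether the 54 were already screened for invasive disease, so loss through histology is only an inference. The RNA quality step after receipt makes some loss plausible, of unknown size.

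**Cases cannot be created.** Tissue is limited to the repository, and the protocol says it will proceed whatever the power. That is a reason to ask for no more samples, but not to leave an unsupported figure in place.

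**Conclusion.** The concern holds for the power statement. The condition behind the claim of more than 80% has probability at most 2.7% with 54 cases, is impossible below 50, and is not expected under the protocol's own distribution. These results need only the protocol's numbers and multinomial sampling; they assume no loss rate.

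The double use of 54 is a real gap in the text, but its effect is uncertain. At an assumed 10% loss (49 cases), the illustrative alternatives lose about 3 to 4 points of power for the primary test; at an assumed 20% loss (43 cases), about 8 to 10. These figures depend on the chosen alternatives and on how the other subtypes move.

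A reader might go further and conclude that falling below 50 cases breaks the primary analysis. The documents do not support this: the 10-per-subtype premise belongs to the pairwise subtype comparisons, and the case-versus-control chi-square has no such threshold.

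**What to change.** In the power paragraph, delete the premise of 10 samples per subtype and the sentence claiming still greater power. Replace them with power or precision for the primary case-versus-control chi-square:

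- Use the expected 50/20/20/10% distribution, and name the alternative, including how the remaining subtypes change.
- Give the result at 54 and at a stated evaluable number. If 80–90% of samples yield usable arrays, an assumption to be replaced by the laboratory's own rate, this is 54 × 0.8 = 43 to 54 × 0.9 = 49.
- If precision is preferred, give the 95% half-width for a share, 1.96 × √(p(1 − p)/n). For p = 50% this is 13 points at n = 54 and 15 at n = 43; for p = 10% it is 8 and 9 points.

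In the methods text and the materials request, label 54 as samples to be obtained, and use a separate term for cases analysed.

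The cost is a few sentences and a less favourable stated figure. No extra samples or change of design are needed.

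### The stated >80% power cannot come from a chi-squared test with 10 samples per subtype at alpha 0.005, and the primary case-versus-control comparison has no stated power

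*Protocol*

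**What the plan says.** The last paragraph of Statistical and Analytic Plans in the Protocol holds the only power statement.

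- It sets up its most diffuse case with "if there are at least 10 samples per subtype (5" subtypes in all), and claims that "there will be a >80% power to detect a 2-fold difference between any of the two groups using Chi-squared analysis".
- Its inputs are "A coefficient of variation of 50% and alpha = 0.005", the latter explained as "alpha = 0.005 (.05/10, to adjust for 10 comparisons between 5 groups").
- It then adds: "Since we expect there to be 50% with the Luminal A subtype designation, there will be even greater power" to make the conclusion valid.
- It does not say which quantity differs 2-fold, or from what base.

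Specific Aim 1 expects that "approximately 50% will be Luminal A, 20% will be Luminal B, 20% will be Basal, and 10% will be Her 2"-positive. The primary endpoint is the subtype distribution compared with spontaneous breast cancer. The first paragraph of Statistical and Analytic Plans assigns it a chi-square test of secondary against primary cancers: 54 cases and 1,619 controls. No power is given for that test.

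**The concern.** Three things do not fit together.

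1. The variability input describes a continuous measure, while the named test is for counts.
2. Ten against ten at alpha 0.005 is very small for a difference in proportions, so >80% is implausible for the test named.
3. The groups being compared are subtypes within the cases, which is not the primary comparison.

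The working hypothesis is that the subtype mix in irradiated survivors resembles that of the general population. A non-significant primary test would therefore be read as support. A reader who trusts the >80% would take that reading further than the data allow, above all for shifts the design is unlikely to detect.

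**Working it through.** **Inputs from the Protocol.** n = 10 per subtype; five subtypes, so 5 × 4 / 2 = 10 pairs and alpha = 0.05 / 10 = 0.005 (this split is right); 2-fold difference; CV 50%; 54 cases; 1,619 controls; expected mix 50/20/20/10.

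**Assumptions.** Two-sided testing. For proportions, 2-fold means p v 2p, with p up to 50%. The primary test's alpha is not stated; 0.05 is used.

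**1. The plan's figure by its named test.** Pearson chi-squared on 1 df has critical value 7.88 at alpha 0.005. Power is the sum of binomial probabilities over all 10 v 10 tables beyond it.

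| Proportions | Exact power | n per group for 80% (normal approximation) |
|---|---|---|
| 10 v 20% | 0.2% | 338 |
| 20 v 40% | 2.2% | 139 |
| 30 v 60% | 5.2% | 72 |
| 40 v 80% | 12.9% | 39 |
| 50 v 100% | 37.7% | 19 |

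The last row can be checked by hand. One group is 10/10 and the other x/10, so chi-squared = 20(10 − x)/(10 + x). At x = 4 this is 8.57 (significant); at x = 5 it is 6.67 (not). Power = P(X ≤ 4 | n = 10, p = 0.5) = 386/1024 = 37.7%.

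Other two-sided methods at the same extreme give 17% (Yates or Fisher), 39% (normal approximation), 41% (noncentral chi-squared), 62% (likelihood ratio) and 76% (arcsine). None reaches 80%.

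If 2-fold instead means one subtype twice as frequent as another (10 v 20 samples, a binomial test on 30 split 1:2), power at alpha 0.005 is about 17%.

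**2. The plan's figure from its CV.** Two-sample t-test, n = 10 per group, 18 df, noncentrality d × √(10/2), alpha 0.005. Set the lower mean to 1 and the higher to 2.

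- Common SD of half the lower mean: d = (2 − 1)/0.5 = 2.0, power 87.8%.
- CV 50% in both groups, raw scale: SDs 0.5 and 1.0, root mean square √0.625 = 0.791, d = 1.265, power 38.8%.
- CV 50% in both groups, log scale: SD = √ln(1.25) = 0.472, d = ln 2 / 0.472 = 1.467, power 54.6% (87.3% if alpha were 0.05).

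Of these readings of a 50% CV, only the first gives more than 80% at the stated alpha, and it is not a constant CV: the higher group's would be 0.5/2 = 25%.

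**3. The primary test.** Chi-square on 3 df, 54 v 1,619, alpha 0.05, controls at 50/20/20/10. One subtype is moved from b to c in the cases and the others multiplied by (1 − c)/(1 − b). Basal doubling, for example, gives 37.5/15/40/7.5. Power by multinomial simulation:

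| Shift in cases | Power |
|---|---|
| Luminal A 50 to 25% | about 91% |
| Luminal B or basal 20 to 40% | about 81% |
| HER2 10 to 20% | about 48% |
| Luminal B or basal 20 to 10% | about 28% |
| HER2 10 to 5% | about 10% |

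If 10 to 30% of samples proved unusable (an assumed range, 49 down to 38 evaluable), power for basal doubling would be about 78% down to 66%.

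**4. Even distribution within the cases.** Goodness of fit of 50/20/20/10/0 against equal fifths, 4 df, n = 54, alpha 0.005. Noncentrality = 54 × (0.09 + 0 + 0 + 0.01 + 0.04)/0.2 = 37.8; power is above 99%.

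**The case against.** The best defence is that 54 is set by available tissue, not by this calculation, and that the paragraph itself says the study is worth doing whatever its power. The number also has a plausible source: a t-test with d = 2 gives 88%, so the defect may be a misnamed test and an unnamed measure. All of that stands. It shows that no sample size depends on the figure, and that naming the measure is a legitimate repair. It does not make the figure true for the test named.

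The 38% ceiling is also specific to 10 v 10 and the exact two-sided Pearson test. Larger or unequal groups can do better: 10 v 27 reaches 94.5% at 50 v 100%. The safe wording is that 80% is not reached at the stated sizes.

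A reader might infer more than the Protocol supports:

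- **That 10 per subtype contradicts Aim 1**, whose mix gives 54 × 10% = 5.4 HER2 cases and none in a fifth group. The figure is a labelled hypothetical, and the same paragraph then states the expected mix.
- **That concentration in Luminal A lowers power for HER2 pairs.** This is not general. With 5 HER2 v 27 Luminal A, exact power is 24% at 40 v 80% and 81% at 50 v 100%, against 13% and 38% at 10 v 10. With Luminal A as the lower proportion at 40 v 80%, it is 7%.
- **That the greater-power sentence is simply false.** It can refer to the paragraph's opening question, whether subtypes are evenly spread or dominated by one or two. On that question it is right (step 4).
- **That Luminal B is less well powered than basal.** Both start at 20% and have the same power; the direction of the shift makes the difference.
- **That normal-like tumours should be set aside as unclassified.** The Protocol names five subtypes. The four-group calculation above only follows Aim 1's expected shares, which sum to 100% over four.

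**Conclusion.** The power statement is wrong as written. For the named test, sizes and alpha, exact power is 13% or less for base proportions up to 40% and 38% at the extreme, against a claimed >80%. This rests on reading 2-fold as p v 2p; the relative-frequency reading fails as well. The stated inputs fit a comparison of means, and then only with a common SD of half the lower mean.

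The statement also leaves the primary comparison without a power figure. On the plan's own expected mix and an assumed alpha of 0.05, that comparison is reasonably powered for a halving of Luminal A or a doubling of Luminal B or basal. It is not adequately powered for a 2-fold HER2 change in either direction, or for a halving of Luminal B or basal. These figures depend on the remaining subtypes rescaling in proportion and on all 54 samples being evaluable.

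**What to change.** 1. Remove the >80% chi-squared statement. If a continuous expression measure was meant, name it and its t-test, and state the SD assumption behind the 88%.
2. Add the power of the case-versus-control chi-square with its alpha, explicit proportions and direction of shift, as in the step 3 table.
3. State that a 2-fold HER2 change in either direction, and a halving of Luminal B or basal, are not adequately powered, so a non-significant result does not show that the distributions match.
4. Limit the greater-power sentence to whether subtypes are evenly distributed within the cases, and cite the goodness-of-fit calculation.
5. Optionally, repeat the primary-test power for 38 to 49 evaluable samples, labelled as an assumption.

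The cost is Protocol wording. Samples, tests and conduct do not change; the stated power becomes less favourable for some shifts.
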